7. SAFETY ASSESSMENTS

For yoga, the only expected adverse event is:

- Physical injury (mild). This includes mild aches or pain during or shortly after yoga classes.

Risks of study participation include:

- Perception of coercion
- Loss of privacy or breach of confidentiality
- Increased distress due to intervention or assessment procedures
- Physical injury

Risks and measures to reduce those risks are detailed below.

Perception of coercion to participate in the study. The risk of potential coercion will be minimized by following standard procedures for obtaining informed consent. All patients will be instructed that their decision as to whether to participate in the study will not influence their current or Protocol Version 2.8

future standing with Butler Hospital, CODAC, BMC, Cleveland Clinic or sites external to any of these facilities. They will also be informed of their right to withdraw from the study at any time.

Confidentiality and loss of privacy. Breach of confidentiality is highly unlikely because all data are identified only by numeric code and are stored in locked file cabinets or secure databases. A master list of names and numbers is kept in a separate database and is used to facilitate the collection of follow-up data. Only research staff at the relevant sites will have access to the master list linking names and code numbers. All staff are or will be fully trained in relevant ethical principles and procedures, particularly around confidentiality and protection of human subjects. All assessment and treatment procedures will be closely supervised by the project's professional staff. All recordings will be erased upon completion of data analysis. The investigative team will strictly adhere to the guidelines for research outlined by the Butler Hospital's Institutional Review Board (IRB), Rhode Island State law, and the DHHS Federal Policy for the Protections of Human Subjects (45 CFR, Part 46).

All data collected will be entered into an electronic database which is stored on a secure server (REDCap) that is backed up on a daily basis. Patient identifying information will be password protected and stored on a secure server. All paper files will be kept in a locked filing cabinet. Audio recordings will be stored on a secure server or kept in a locked filing cabinet. No subject will be identified in any report of the project.

REDCap is a secure, web-based application developed by Vanderbilt University for building and managing surveys and databases. It is primarily designed to support online or offline data capture for research studies, quality improvement, and operations. REDCap provides easy data manipulation (with audit trails for reporting, monitoring and querying patient records), real-time data entry validation, and an automated export mechanism to common statistical packages.

Care New England's instance of REDCap is hosted within the Care New England data center in Warwick, RI. This REDCap instance is role-based and is fully integrated with CNE's Active Directory structure. It enjoys 24/7/365 enterprise-level support and security inherent to CNE's HIPAA-compliant data center. Network transmissions (data entry, survey submission, and web browsing) to and from REDCap are protected via TLS 1.2 encryption. REDCap's data is stored on encrypted servers within CNE's data center.

The REDCap Consortium is composed of thousands of active institutional partners in over one hundred countries who utilize and support REDCap. REDCap was developed specifically around HIPAA-Security guidelines, and more information about the consortium and system security can be found at <http://www.projectredcap.org/>.

Due to the nature of text messaging technology and email, there is a small, but potential, privacy risk when communicating through text messages or email messages. Text or email message communications are not encrypted and therefore this information can be read if intercepted while in transit. Although we have a strict patient confidentiality policy there is a possibility for the text messaging or email communications to be intercepted or accessed without the participant's authorization. This will be made clear in the informed consent process, and we will remind participants of the risks of sending sensitive information by text or email. It is important to note that study staff will only be conveying general information by text messaging or email. Study staff will not send confidential or sensitive personal information by text message at any time. Email messages may include links to REDCap. Text messages will be sent from a dedicated password-protected study cell phone; email will be sent from a carene.org account or an account at the site (e.g., BMC.org). The loss of privacy is a

serious risk, but we believe that it is highly unlikely as we have extensive experience taking measures appropriate to safeguarding confidential information.

For streaming video classes, we will choose a secure, HIPAA compliant video service such as Zoom. Classes will be monitored to ensure that people who should not be a part of the class do not enter electronically. We will ask participants to find as private a space as possible for their real-time yoga classes, and we will make sure all participants are aware of the possibility of a breach of privacy if another participant discloses their identity outside of the context of class. (This breach of privacy is possible in in-person classes as well). All participants will be asked to keep the names of other participants in their class confidential.

Protections against increased distress due to assessment or intervention procedures. The risks of possible distress due to the assessment and treatment procedures will be minimized by: a) using assessments and procedures which have been widely used in previous clinical and research studies; b) training yoga instructors in how to minimize and manage distress that may occur in class; and c) having study investigators with medical or psychology degrees available to counsel participants should they report experiencing distress.

In the Endpoint Qualitative Interview –Intersectional Stigma, participants will be reminded that they do not have to answer any question that they do not want to answer. In addition, the interview template will be designed with an emphasis on strengths and resiliency in navigating difficult experiences. The interviewer will be a clinical psychologist trained in conducting qualitative interviews of a sensitive nature, and will be able to address any distress or concerns that may emerge during the interview, including follow-up referrals for behavioral health in the unlikely event this should be necessary.

Protections against risk of physical injury. The risk of physical injury will be minimized by: a) excluding participants with contraindicated medical conditions; and b) requiring all instructors to be certified yoga teachers with experience in directing people in how to achieve yoga postures without physical injury; and c) giving all participants a guidebook that explains safer ways to engage in yoga practices. Class content will be designed to accommodate the needs of yoga-naïve students who are not currently physically active. By presenting modifications of all postures, and by using props (e.g., chairs), the risk for injury will be minimal. We will not use postures in this study that are most commonly associated with adverse events, such as headstands, shoulder stands, or handstands.

Potential Benefits

The direct benefits to participants include the possibility of enjoyment of yoga classes and decreased pain. By participating in the clinical research project, participants may benefit from the additional contact with research staff that they will receive. The participant will be contributing to scientific research on optimizing dosage of yoga to the greatest degree possible in an OAT population. Given this level of risk(s) to the patients and the likelihood that some will benefit and the even greater possibility of benefits to the larger population of individuals in OAT through scientific gain, the risk/benefits ratio seems favorable.

Risk-Benefit Ratio.

We believe that most serious risks (e.g., loss of confidentiality, major psychological distress due to study participation, or serious physical injury due to yoga participation) to subjects are very unlikely. We have attempted to minimize these risks (described above). While some risks may be more

likely to occur (e.g., minor, transient psychological distress), these risks are much less serious. Therefore, the potential benefits of the proposed study seem to outweigh the potential risks of this study for the individual participants.

7.1 Specification of Safety Parameters

Table 2 Assessment and Management of Safety Issues

Safety Issue	How assessed	When Assessed in Phase 2/Phase 3	Relevant Research Staff Actions
Injuries due to yoga	Structured self-report	Weekly during first 3 months	Follow until resolution; may result in changes to yoga instructor manual
Other AEs	SAFTEE Participant report to research staff	M3 BL, M3, M6*, M12* Any point	If related to study participation, follow resolution; potential changes to procedures particularly if AE is also unexpected

*Phase 2 only

7.2 Methods and Timing for Assessing, Recording, and Analyzing Safety Parameters

See Table 2

7.3 Adverse Events and Serious Adverse Events

Adverse Event (AE) definition: An adverse event (AE) is any unfavorable and unintended diagnosis, symptom, sign (including an abnormal laboratory finding), syndrome or disease which either occurs during the study, having been absent at baseline, or if present at baseline, appears to worsen. Adverse events are to be recorded regardless of their relationship to the study intervention.

Serious Adverse Event (SAE) definition: A serious adverse event (SAE) is one that meets one or more of the following criteria:

- Results in death
- Is life-threatening (places the subject at immediate risk of death from the event as it occurred; includes a suicide attempt or drug overdose)
- Results in inpatient hospitalization or prolongation of existing hospitalization
- Results in a persistent or significant disability or incapacity
- Results in a congenital anomaly or birth defect

An important medical event that may not result in death, be life threatening, or require hospitalization may be considered an SAE when, based upon appropriate medical judgment, the event may jeopardize the subject and may require medical or surgical intervention to prevent one of the outcomes listed in this definition.

Study staff will record all reportable events with start dates occurring any time after informed Protocol Version 2.8

consent is obtained at least until the final day of study participation. Each time participants attend a yoga class, we will inquire about injuries due to yoga. For all participants in either the Phase 1 or 2, at Month 3 (end of intervention), study staff will administer the SAFTEE in order to inquire about the occurrence of AE/SAEs during the previous 3 months. This allows us to systematically assess the number of adverse events, severity, and resulting impairment. Finally, any time a participant reports an adverse event to any staff member, a research assistant will contact the participant to ascertain information for recording of the adverse event. For adverse events ascertained by any of these three possible methods, the research assistant gets information on what happened, start and stop dates, severity, functional impact, interactions with healthcare professionals, perceived cause, and possible relation to study participation. With this information, site PIs or Co-Is, with input from MPIs if needed, will code severity, causal relationship, and whether the event was expected. If necessary, staff will seek further information from the participant or other sources before coding. AEs will be coded on a weekly basis. Any potential SAE will be immediately reviewed by one of the MPIs or site PIs (or a qualified designee in their absence) and coded; this coding will subsequently be reviewed by the Safety Monitoring Committee (SMC).

7.4 Reporting Procedures

Reporting for Multi-Center Trials

The site PI must immediately report to the coordinating center MPIs any serious adverse event that is possibly study related within 48 hours of PI awareness of the event. Unrelated SAEs must be reported within 7 days.

The site PI must also report any unanticipated problems (see below) within 48 hours of PI awareness of the event. The Site PI must also report any protocol violations to the coordinating center PI within 7 days of PI awareness. Participating centers must also submit all reports to their local IRB in accordance with their institutional policies.

AE/SAE Reporting

SAEs that are unanticipated, serious, and possibly related to the study intervention will be reported to the Safety Monitoring Committee (SMC), IRB, and NCCIH in accordance with requirements. We will use the Butler Hospital IRB-approved AE report form.

- Unexpected fatal or life-threatening SAEs related to the intervention will be reported to the IRB, NCCIH Program Officer, and SMC within 3 days of the investigator becoming aware of the event. Other serious and unexpected SAEs related to the intervention will be reported within 7 days. These timeframes follow guidance from NCCIH and are consistent to local IRB policies.

Anticipated or unrelated SAEs will be handled in a less urgent manner but will be reported to the SMC, IRB, and other oversight organizations in accordance with their requirements, and will be reported to NCCIH on an annual basis.

- Unrelated SAEs that are fatal or life threatening must be reported to the Butler Hospital IRB within 7 days of the investigator becoming aware of the event.
- Unrelated SAEs that are not fatal or life-threatening must be reported to the Butler Hospital IRB annually.

All other AEs documented during the course of the trial will be reported to NCCIH on an annual basis by way of inclusion in the annual report and in the annual AE summary which will be provided to NCCIH and to the SMC. The SMC Report will state that all AEs have been reviewed.

Unanticipated Problem Reporting

OHRP considers *unanticipated problems*, in general, to include any incident, experience, or outcome that meets **all** of the following criteria:

1. Unexpected (in terms of nature, severity, or frequency) given (a) the research procedures that are described in the protocol-related documents, such as the IRB-approved research protocol and informed consent document; and (b) the characteristics of the subject population being studied;
2. Related or possibly related to participation in the research (in this guidance document, *possibly related* means there is a reasonable possibility that the incident, experience, or outcome may have been caused by the procedures involved in the research); and
3. Suggests that the research places subjects or others at a greater risk of harm (including physical, psychological, economic, or social harm) than was previously known or recognized.

Incidents or events that meet the OHRP criteria for unanticipated problems require the creation and completion of an unanticipated problem report form. OHRP recommends that investigators include the following information when reporting an adverse event, or any other incident, experience, or outcome as an unanticipated problem to the IRB:

- Appropriate identifying information for the research protocol, such as the title, investigator's name, and the IRB project number;
- A detailed description of the adverse event, incident, experience, or outcome;
- An explanation of the basis for determining that the adverse event, incident, experience, or outcome represents an unanticipated problem;
- A description of any changes to the protocol or other corrective actions that have been taken or are proposed in response to the unanticipated problem.

To satisfy the requirement for prompt reporting, unanticipated problems will be reported using the following timeline:

- Unanticipated problems that are not SAEs will be reported to the IRB, SMC, and NCCIH within 14 days of the MPIs becoming aware of the problem.
- See above for SAE reporting.

All unanticipated problems should be reported to appropriate institutional officials (as required by an institution's written reporting procedures), the supporting agency head (or designee), and OHRP within one month of the IRB's receipt of the report of the problem from the MPIs.

7.5 Follow-up for Adverse Events

Any SAEs related study participation will be followed for outcome information until resolution or stabilization. Follow-up reports will be submitted to the IRB, SMC, or NCCIH as required in each specific instance.

7.6 Safety Monitoring

NCCIH requires that all Human Subjects research studies undergo independent monitoring, and NCCIH Program Officials will provide specific guidelines to the PI for the study.

8. INTERVENTION DISCONTINUATION

Participants will be discontinued from an intervention in the following circumstances:

- If a participant, their primary care provider, or their OAT provider does not believe it is in the best interest of the participant to continue. As soon as an MPI or site PI is informed of this, they will speak with the participant about discontinuation. There may be circumstances (e.g., worsening pain, an injury in yoga class) when the MPI reaches out to a primary care provider, OAT provider to actively inquire if they have concerns about the participant continuing to participate.
- If a participant chooses to discontinue attendance.
- If one of the MPIs or site PIs, in consultation with the relevant instructor, finds the participant to be so disruptive to the rest of the class that they have a repeated and substantive negative impact on the other participants.
- If a participant knowingly compromises the confidentiality of another class participant.

Participants will continue with subsequent assessments with their permission. Assessment schedule and assessments used will not change.

9. STATISTICAL CONSIDERATIONS

9.1 General Design Issues

The overall goal of this balanced factorial optimization trial is to develop a yoga intervention package that is optimized for achieving maximal “dosage” of yoga received.

We will document feasibility and acceptability of a yoga program for chronic pain at two new recruitment sites and develop a yoga intervention optimized for maximizing the dose of yoga received. We will also examine mechanisms by which components may serve to increase yoga dosage received.

9.2 Sample Size and Randomization

In RCTs a conclusion is made regarding the effect of intervention based on rejecting the null hypothesis with Type I error $<$ some predefined α . In contrast, in an optimization trial, a decision is made to include or exclude specific components in an intervention that will be tested in a future RCT. In this scenario, Type II error may be as pernicious as Type I error. Therefore, based on recommendations of Collins ³⁰ this study will be powered with $\alpha/2 = .10$. Because intervention effects are uncorrelated (or nearly uncorrelated if the design is not perfectly balanced), the alpha will not be corrected for multiple comparisons and all effects have equal statistical power. Assuming approximately 17% attrition for our primary outcome of dosage, we estimated power for $n= 158$ (192-34). To estimate the minimum detectable effect size we assumed a small correlation ($r = .15$) between

recruitment site and yoga attendance and used the FactorialPowerPlan³¹ macro in R. The proposed design has sufficient power ($1 - \beta > .80$) to detect a standardized difference in means of .40 or larger. Power to detect a medium standardized effect ($d = .50$) is $> .90$.

9.2.1 Treatment Assignment Procedures

Eligible individuals who consent to participate will be randomly assigned to one of 16 study conditions (Table 3). Our study statistician who has no contact with study participants and will have no access to outcome data until database lock, will create randomization tables using Microsoft Excel and upload to our data collection system (REDCap) prior to the start of recruitment for Phase 1. Because this is a 16-cell design, we will not stratify by any variables at baseline. Block size is effectively 12 (i.e., number of participants per cell.)

Study staff will not have access to randomization tables. When a person is deemed eligible, study staff will verify the stratification variables in REDCap and then click the “RANDOMIZE” button.

For Phase 1, given there are few participants, we want to ensure that each site has an opportunity to pilot each intervention component and certain key combinations.

Table 3. Balanced Factorial Design Assessing Four Candidate Intervention Components

Cell	COMPONENT				Phase 1		Phase 2	
	1	2	3	4	n	n		
1	No	No	No	No	1	12		
2	No	No	No	Yes	1	12		
3	No	No	Yes	No	1	12		
4	No	No	Yes	Yes	1	12		
5	No	Yes	No	No	1	12		
6	No	Yes	No	Yes	1	12		
7	No	Yes	Yes	No	1	12		
8	No	Yes	Yes	Yes	2	12		
9	Yes	No	No	No	1	12		
10	Yes	No	No	Yes	1	12		
11	Yes	No	Yes	No	1	12		
12	Yes	No	Yes	Yes	2	12		
13	Yes	Yes	No	No	1	12		
14	Yes	Yes	No	Yes	1	12		
15	Yes	Yes	Yes	No	2	12		
16	Yes	Yes	Yes	Yes	2	12		

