3. STUDY DESIGN

In Phase 1, we will enroll 10 participants at each recruitment site (n=20). The purpose of Phase 1 (MOST Preparation Phase) is to allow us to establish and refine procedures at these new sites and document aspects of feasibility, including our ability to a) recruit participants; b) train yoga teachers to fidelity; c) randomize participants to intervention components and correctly administer these components; d) run classes; and e) collect follow-up assessments. Enrollment period for this phase will last approximately 4 months.

In Phase 2, we will conduct a fully powered optimization trial. We will enroll 192 participants, planning to role approximately equal numbers of participants in both sites. In both phases, all participants will receive the core yoga intervention (12 weeks of weekly manualized yoga classes), with random assignment to the 4 key intervention components. Participants will be patients enrolled in methadone or buprenorphine/naloxone treatment with chronic pain. Enrollment period for this phase will last approximately 2 years.

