9.6 Data Analyses

Phase 1 Data Analysis: See Section 9.5.1

Phase 2 Data Analysis: We plan to assess 4 candidate intervention components for possible inclusion in an optimized intervention that will be evaluated in a future RCT. To do so, we will use a balanced factorial ANOVA illustrated in Table 2. Each component will have two conditions producing a $2^4 = 16$ cell design with 4 main effects, 6 possible 2-way interactions, 3 possible 3-way interactions, and 1 possible 4-way interaction. In a fully balanced design using effect coding (not dummy coding), all effects in the model are uncorrelated and the n for each condition for all effects is N/2 (i.e., 96 without attrition; 79 estimated with 17% attrition for this primary outcome). Note that specific cells are not compared against other specific cells.

We will use a general linear model with each candidate component coded using effect (1 vs -1) coding. Recruitment site, sex, age, and OAT type will be covariates. The pragmatic exigencies of field research will likely result in imperfect balance (e.g., individual cells may have slightly varying n). However, we anticipate only very small variations in cell sizes and thus estimated model coefficients will be nearly, but not perfectly, uncorrelated.

To augment traditional frequentist statistics and facilitate interpretation we will calculate the Bayes factor. Based on the observed data, a Bayes factor estimates the strength of evidence supporting one hypothesis (model) in favor of a competing hypothesis (model).³²

We will track which classes each participant attends, and who teaches each class. As a sensitivity analysis, we will include not only site as a fixed effect, but also teacher. We will include a dummy variable for each teacher to represent whether or not the participant had exposure to that particular teacher (i.e., took at least one class with that teacher).

Determination of Final Intervention Components:

Goal: To determine which components will be included in the final, optimized intervention package.

Components:

All participants: attendance at 1 class (with 2 time choices) per week; materials for personal practice

1. Personal practice videos featuring study yoga teachers
2. Initial and 1-month 1:1 session with a yoga teacher
3. Text messages cuing personal practice
4. Monetary incentives for class attendance

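### Does the stated block size of 12, with a stray reference to stratification variables, undermine the balanced 16-cell design?

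*Combined protocol and SAP*

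**What the plan says.** Section 9.2.1 has participants "randomly assigned to one of 16 study conditions (Table 3"), and Table 3 gives 12 places to each of the 16 cells in Phase 2. The statistician prepares the tables in Excel and uploads them to REDCap before Phase 1 recruitment starts. On restriction the section says "Because this is a 16-cell design, we will not stratify by any variables at baseline", followed by "Block size is effectively 12 (i.e., number of participants per cell". The next paragraph describes the randomizing step: "study staff will verify the stratification variables in REDCap" and then press the button.

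Section 3 describes Phase 2 as "planning to role approximately equal numbers of participants in both sites". Section 9.6 fits a general linear model with effect coding and with recruitment site, sex, age and OAT type as covariates. It accepts that balance will be imperfect but says "we anticipate only very small variations in cell sizes". Section 9.2 likewise treats the effects as uncorrelated or nearly so.

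**The concern.** A permuted block that gives 16 cells equal shares must hold a multiple of 16 places, and 12 is not one. The plan has put the cell quota where the block size belongs. It also denies stratification and then refers to stratification variables, so a reader cannot tell whether site is a stratum.

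If the scheme is one unblocked list, equal cells are guaranteed only when exactly 192 people are randomized, and nothing balances cells within site or over roughly two years of enrollment. That could matter for three reasons:

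- The uncorrected alpha and the equal power for all effects rest on near-orthogonality.
- The power calculation assumes that site is correlated with attendance.
- Section 9.4.2 lists recruitment difficulty as a ground for stopping early.

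The number of cells does not by itself rule out stratifying by site, since 96 per site is six blocks of 16.

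**Working it through.** **Inputs.** There are 16 cells of 12 (Table 3). Section 9.2 gives 192 randomized, 158 analyzed (192 − 34) and a target difference of 0.40. Alpha is taken as 0.10 two-sided, in line with the p < .10 rule in Section 9.6. Two sites of 96 with random order of arrival are assumed. Cell ranges below are median smallest to median largest counts from simulation.

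**1. The plan's own figures.** 16 × 12 = 192, and 158/2 = 79 per component level. Power is approximately Φ(d√(n/2) − 1.645).
- d = 0.40: 0.40 × √39.5 = 2.514, and Φ(0.869) = 0.808.
- d = 0.50: 0.50 × √39.5 = 3.142, and Φ(1.497) = 0.933.

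Both agree with the stated values above .80 and .90.

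**2. What the sentence can mean.** 12 is not a multiple of 16, so it is not a block size for equal allocation. The parenthesis equates it with the number per cell, and Table 3 shows the same 12. The natural reading is one permuted list of 192, that is, a real block of 192.

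**3. Full enrollment.** The full factorial model plus site was fitted to 2,000 simulated allocations per scheme. Variance inflation of a main effect divides the 79.

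| Scheme at N = 192 | Cells overall | Cells within site | Inflation, median / 95th percentile | Power, median / at 95th percentile |
|---|---|---|---|---|
| Single list | 12 each | 3 to 9 | 1.002 / 1.023 | 0.807 / 0.800 |
| Blocks of 16, unstratified | 12 each | 3 to 9 | 1.002 / 1.023 | 0.807 / 0.800 |
| Blocks of 16 within site | 12 each | 6 each | 1.000 / 1.000 | 0.808 / 0.808 |

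Blocking alone does nothing for balance within site. Stratifying secures it, for a median gain of 0.1 point of power.

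**4. The analyzed sample.** 158 is what remains after attrition, not a number randomized. Dropping 34 at random from a balanced 192 gives the same distribution of cell counts as the first 158 rows of a permuted list. The SD of a component-level count is √(158 × 0.25 × 34/191) = 2.65 in both cases. Cells range from 7 to 12 under the single list and under site-stratified blocks alike. Random loss from a perfect 192 alone inflates the variance by a median of 1.017 (power 0.802), which is more than the single list adds. With site in the model and a noncentral t (0.804 if perfectly balanced), power is 0.796 for the single list and 0.798 for site-stratified blocks.

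**5. Early stopping on the single list**, with the same proportion lost (analyzed per level = N × 158/192 ÷ 2):

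| N randomized | Cells overall | Power if perfectly balanced | Median power, single list | Loss from imbalance |
|---|---|---|---|---|
| 180 | 10 to 12 | 0.785 | 0.782 | 0.3 points |
| 160 | 8 to 12 | 0.742 | 0.734 | 0.8 points |
| 128 | 5 to 11 | 0.658 | 0.639 | 1.9 points |
| 96 | 3 to 9 | 0.553 | 0.518 | 3.5 points |

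At 96, the shortfall itself costs 0.808 − 0.553 = 25.5 points, about seven times the imbalance loss.

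**6. Changing the list midway.** Section 6.2.7 already refers to active Phase 2 participants. Suppose the single list has run to 96, with cells from 3 to 9. Six blocks of 16 for the remaining 96 add 6 to every cell and give 9 to 15. Leaving the list alone returns every cell to 12.

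**The case for a change.** The best case for acting is that sequence generation is a basic item for judging a randomized trial, and Section 9.2.1 does not state it correctly. The two stratification statements conflict within one section. Phase 1 is meant to let each site try every component, which suggests that site may have entered the allocation. Describing the list would cost almost nothing, and site-stratified blocks would have given better balance by site, over time and under early stopping.

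The description of the fault stands: 12 is a quota, the staff instruction conflicts with the sentence on stratification, and a single list gives no assurance of balance within site or over time. The consequence does not follow. The text is muddled but can be carried out; with no strata, the verification step is simply empty. Site is in the primary model in either case, so the analysis does not wait on the answer. Chance imbalance by site or time costs a little precision but does not bias a randomized comparison.

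Leaving a 16-arm trial unstratified and adjusting for covariates is also a fair choice. Site, sex and OAT type together would give 2 × 2 × 2 = 8 strata averaging 192/8 = 24, which is not a multiple of 16. Even site is not a clean two-level factor: under Section 4.3, Cleveland Clinic recruits pass to Butler Hospital after consent, and community sites may also contribute participants.

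**Conclusion.** No change follows. The section mislabels a cell quota as a block size and carries an instruction that does not fit an unstratified design. Both are clerical, and the statistician who holds the REDCap table can report the list actually used. At the planned size the single list costs 0.1 to 0.2 points of power compared with site-stratified blocks. The loss is 0.8 points if enrollment stops at 160, and it reaches 3.5 points only if enrollment halves, when lost sample size dominates.

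These figures assume two equal sites, random order of arrival, loss unrelated to cell, and two-sided alpha of 0.10. If site was in fact a stratum, balance within site is better than shown here and the analysis model is unchanged.
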